# 4.0 Study Design

4.1 Describe and explain the study design (e.g. case-control, cross-sectional, ethnographic, experimental, interventional, longitudinal, and observational).

#### Response:

This is a single center, double blinded, randomized controlled trial with two treatment arms to be performed at a single tertiary care children's hospital. Patients will be randomized within 2 hours of initiation of care to receive DKA management using intravenous fluids containing primarily normal saline or lactated ringers. All other aspects of DKA management will be the same in each arm, per the institution protocol.

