#### Response:

All children with Diabetic ketoacidosis presenting to the John R. Oishei Children's Hospital (OCH) emergency department (ED) or transferred directly from outside facility to the pediatric intensive care unit (PICU) will screened for eligibility. Patients who are directly admitted to the PICU will represent 10% of the study sample with the remainder coming from the ED. As not all children in DKA are admitted to the PICU from the ED, it is estimated that approximately an additional 200 patients will be screened in the ER to achieve the target study size. In total, we anticipate screening approximately 310 patients with DKA for this study. 5.3 Justify the feasibility of recruiting the proposed number of eligible subjects within the anticipated recruitment period. For example, how many potential subjects do you have access to? What percentage of those potential subjects do you need to recruit?

Response:

Using historical patient volume data, it is estimated that approximately 2 years will be required to reach the target enrollment number.

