#### Response:

Exclusion criteria:

- 1. Physician discretion for any reason not listed here
- 2. Septic or hypovolemic shock
- 3. Signs of life-threatening cerebral edema or multi-organ failure upon presentation to the emergency room or pediatric intensive care unit
- 4. More than 2 hours since arrival to the PICU or from first provider contact in the emergency room
- 5. Pregnancy
- 6. Type II DM
- 7. Elevated anion gap metabolic acidosis from another source other than ketoacidosis
- 6.3 Indicate specifically whether you will include any of the following special populations in your study using the checkboxes below.

*NOTE: Members of special populations may not be targeted for enrollment in your study unless you indicate this in your inclusion criteria.* 

- Adults unable to consent
- Individuals who are not yet adults (infants, children, teenagers)
- Pregnant women
- □ Prisoners
- 6.4 Indicate whether you will include non-English speaking individuals in your study. **Provide justification if you will exclude non-English speaking individuals.**

In order to meet one of the primary ethical principles of equitable selection of subjects, non-English speaking individuals may **not** be routinely excluded from research as a matter of convenience.

In cases where the research is of therapeutic intent or is designed to investigate areas that would necessarily require certain populations who may not speak English, the researcher is required to make efforts to recruit and include non-English speaking individuals. However, there are studies in which it would be reasonable to limit subjects to those who speak English. Some examples include pilot studies, small unfunded studies with validated instruments not available in other languages, studies with numerous questionnaires, and some non-therapeutic studies which offer no direct benefit.

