# **10.0 Procedures Involved**

10.1 Provide a description of **all research procedures or activities** being performed and when they are performed once a subject is screened and determined to be eligible. Provide as much detail as possible.

*NOTE:* This should serve as a blueprint for your study and include enough detail so that another investigator could pick up your protocol and replicate the research. For studies that have multiple or complex visits or procedures, consider the addition of a schedule of events table in in your response.

Upon consenting, a copy of the signed informed consent document with the subject name and medical record number will be sent to our inpatient pharmacy by an ED research assistant if the subject is enrolled in the ED. If a subject is enrolled in the PICU, the signed consent will be faxed to the inpatient's pharmacy. Meanwhile, the study protocol will be placed using an electronic order set containing the study DKA management protocol that is identical to the routine management of DKA with the exception of the fluid content per arm. Please refer to study protocol schematic shown in supplement 1.

After receiving the copy of the consent, patients will be randomly assigned a treatment arm (group A or B) and a study ID by the pharmacy following a randomization table generated by a statistician. Each group correlates with a treatment arm assignment visible on a randomization table available only to the inpatient pharmacy personnel. Pharmacy personnel will then provide the appropriate content to the intravenous fluids with a generic label "DKA study fluids with dextrose" and "DKA study fluids without dextrose." The fluids look identical as the bags will be labeled with standardized labelling as "DKA Study fluid with dextrose" or "DKA study fluid without dextrose." The study ID will also be labeled on the bags and typed into the electronic orders by pharmacy. The bags will be properly covered by the labels to ensure complete blinding of the subject and the medical treatment team. The intravenous fluids will be transported to the patients per the regular system used in the ER and PICU.

We anticipate that the eligible patients will be consented within 2 hours of arrival to the PICU or after the first provider makes contact in the ED and shortly thereafter started on continuous infusions of intravenous fluids and insulin per the study protocol.

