#### Response:

Baseline demographic data that will be collected including age, sex, race, comorbid conditions, vital signs, number of hospitalizations for DKA in the preceding 12 months, and date and time of transfer to the PICU.

ED lab data that will be collected include all laboratories obtained in the ED, intravenous fluid volume and type administered, time to start of insulin and PRISM score.

PICU lab data that will be collected include all pH, bicarbonate, anion gap, chloride and beta-hydroxybutyrate levels, sodium, potassium, BUN, creatinine, glucose etc. If the patient remains in DKA after 32 hours after initial ED labs, PICU lab data will be collected until the closest to 36 hours after the initial ED labs were obtained.

Outcomes to be collected include length of stay in the hospital and ICU, resolution of acidosis including time to a serum pH>7.30, bicarbonate >15mg/dl, and normal anion gap.

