#### Response:

Univariate analysis will be used to determine if the subjects in each treatment arm differ at baseline through t-test or Wilcoxon Rank Sum testing for continuous data and Chi-square testing for categorical data. Any differences will be controlled for in the analysis of the primary outcome (length of acidosis) using linear regression. All outcomes will be correlated with the overall chloride load given via intravenous fluids during DKA management. All analyses will be performed using IBM SPSS software, version 25 (Chicago, IL) and SAS (SAS Institute Inc., Cary, NC) with significance set at p<0.05.

17.2 If applicable, provide a power analysis.

*NOTE:* This may not apply to certain types of studies, including chart/records reviews, survey studies, or observational studies. This question is asked to elicit

whether the investigator has an adequate sample size to achieve the study objectives and justify a conclusion.

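### Section 4.1 promises randomization within 2 hours of starting care, but for direct PICU transfers (about 10%) the clock starts on arrival and earlier fluid is not named for collection

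*Combined protocol and SAP*

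**What the plan says.** Section 4.1 describes the design as one in which "Patients will be randomized within 2 hours of initiation of care". It makes no exception for transfers.

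The eligibility rule uses a different time origin. Exclusion criterion 4 in section 6.2 reads "More than 2 hours since arrival to the PICU or from first provider contact in the emergency room". Section 10.1 has the same two starting points but ties them to consent, and only as an expectation: "We anticipate that the eligible patients will be consented within 2 hours of arrival to the PICU or after the first provider makes contact in" [emergency department]. Section 26.3 gives a further form, a goal of enrolling within 2 hours of the first contact with a provider.

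Section 5.2 makes transfers part of the planned sample. Children "transferred directly from outside facility to the pediatric intensive care unit (PICU) will screened for eligibility", and "Patients who are directly admitted to the PICU will represent 10% of the study sample".

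On data, section 10.2 states: "ED lab data that will be collected include all laboratories obtained in the ED, intravenous fluid volume and type administered, time to start of insulin". Its PICU entry lists laboratory values. Section 10.4 gives the hospital system's own electronic record as the source. In the analysis plan (17.1), "All outcomes will be correlated with the overall chloride load given via intravenous fluids during DKA management".

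**The concern.** For a child sent to the PICU from another facility, care starts at that facility. Criterion 4 admits this child up to 2 hours after PICU arrival, however long the outside treatment lasted. So the design as written lacks, for about a tenth of its sample, a property that section 4.1 claims for all of it.

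This touches the mechanism under study. Section 3.1 says that early DKA care tends to involve large volumes of normal saline, and it attributes the hyperchloremic acidosis to such volumes. On that account a transferred child in either arm may already carry a saline load before study fluid begins. Two things are at stake: the size of the contrast between arms in these children, and the accuracy of their chloride load in the 17.1 correlation.

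**Working it through.** **1. Time origins side by side.**
- 4.1: start of care; event timed is randomization.
- 6.2, criterion 4: PICU arrival, or first contact with an ED provider; event timed is eligibility.
- 10.1: the same two origins; event timed is consent, and the limit is only anticipated.
- 26.3: first provider contact; event timed is enrollment, as a goal.

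For a child who starts care in the trial hospital's ED, these nearly coincide. For a direct transfer, 4.1 and 6.2 differ by the whole time spent at the referring facility and in transport. No section bounds that time.

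**2. Number affected.** 0.10 × 104 = 10.4 children, or 0.10 × 52 = 5.2 per arm.

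**3. Data capture.** Section 5.2 introduces the abbreviation ED for the trial hospital's own emergency department. Fluid volume, fluid type and insulin start are listed in 10.2 under ED data only. No field for the referring facility or transport is named, and route of entry is not among the listed baseline items. If fluid given before arrival is left out, the recorded load equals the true load minus that fluid's chloride. The error is an understatement, confined to about 10% of children.

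**4. The plan's own sample size.** Section 17.2 gives 104 children (52 per arm) for 80% power to detect an 8-hour difference in medians at p<0.01. No SD, test or sidedness is stated, and the printed IQRs cannot be read with confidence.
- Reading the second IQR as 3 to 14: SD = 11/1.349 = 8.15 h. Two-sided 0.01 then needs 2 × (3.417 × 8.15/8)², which rounds up to 25 per arm, 50 in total (54 to 58 with a Wilcoxon correction).
- Log-rank with an assumed hazard ratio of 2: 98 events (Schoenfeld) or 106 (Freedman). The second is close to 104, but the protocol names no log-rank test.
- SD that yields exactly 80% with 52 per arm, two-sided 0.01: 8 × √26 / (2.576 + 0.842) = 11.94 h.

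The figure cannot be verified, so the next step takes the stated 80% at face value.

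**5. Dilution.** Let f be the share of the treatment effect lost in transfers, which is an assumption because the documents give no outside treatment times. The average effect is multiplied by k = 1 − 0.10f, with variance held fixed. Then power = Φ(k × 3.417 − z), with z = 2.576 at two-sided 0.01 and 1.960 at two-sided 0.05.

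| f | effect (h) | power at 0.01 | same N at 0.05 | N for 80% at 0.01 |
|---|---|---|---|---|
| 0 | 8.0 | 80.0% | 92.8% | 104 |
| 0.25 | 7.8 | 77.5% | 91.5% | 110 |
| 0.5 | 7.6 | 74.9% | 90.1% | 116 |
| 1 (bound) | 7.2 | 69.1% | 86.8% | 130 |

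Sensitivity at the bound, alpha 0.01: with SD 8.15 h power is 97.3%. In the log-rank variant (104 events, hazard ratio 2) it falls from 83.1% to 72.7%.

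**The case against.** The strongest reply is that admitting transfers is a legitimate choice and costs little. Five arguments support it.

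- Start of care in 4.1 may be shorthand for care at this hospital. That would remove the contradiction, but 4.1 does not say so, and the absence of any limit on outside treatment would remain.
- Section 10.2 is a summary. One of its lists ends in etc., and section 10.3 refers to separate data forms that are not in the document. The list also names no fluid volume for the PICU phase, so it may be illustrative. This stands: a reader might infer that fluid before arrival goes unrecorded, is set to zero, or makes the chloride load false. The documents support only that it is not named for collection and that 17.1 does not say whether it counts.
- A reader might infer that transfers arrive largely resolved. Section 6.1 requires pH below 7.25 and bicarbonate below 15 mmol/L, which limits this, although it does not say when or where the qualifying sample is taken.
- Zero effect in every transfer is a bound, not a forecast. These children receive randomized fluid until the resolution criteria in 10.1 are met, and section 3.1 places the harm of saline partly in the recovery phase.
- Section 17.1 already adjusts for baseline differences. It does so only for differences found by testing, and with about 5 transfers per arm a test would rarely find an imbalance.

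**Conclusion.** The concern holds as a mismatch between the stated and the applied window, together with a gap in the named data. It affects about 10 of 104 children.

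The comparison between arms is not biased: treatment before randomization is a baseline feature, balanced in expectation. A reader might infer otherwise, but the cost is possible dilution and noise. At alpha 0.01, power would be about 75% if transfers lose half the effect and 69% at the bound. These figures rest on the stated 80%, which cannot be reproduced, on a two-sided test and on unchanged variance.

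Applying the same dilution to a design with 80% power at 0.05 gives 71%, but that is not this trial. With this N tested at the 0.05 level of 17.1, the bound is about 87%.

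The chloride-load correlation may be understated for these children. It is not the plan's only approach to mechanism, because section 2.1 also defines resolution three ways to separate the fluid effect from the disease.

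**What to change.** 1. Restate the window in 4.1 to match the criterion actually applied, and reconcile 6.2, 10.1 and 26.3 with it, naming both the time origin and the event timed.
2. Record fluid type, fluid volume and insulin start before randomization for every child, including at the referring facility and in transport. State in 17.1 that this fluid counts in the chloride load.
3. Pre-specify the last pH or bicarbonate before study fluid, which 10.2 already collects, as a covariate in the primary model. This replaces adjusting only for baseline differences found by testing.
4. Optionally, add a sensitivity analysis without direct transfers.

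The cost is a few data fields and a few sentences. The real downside is that transfer records may be incomplete for a few children, so the plan should say how missing values before arrival are handled.

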# 5.0 Local Number of Subjects

5.1 Indicate the total number of subjects that will be enrolled or records that will be reviewed locally.

#### Response:

We plan to enroll 104 subjects in the study with 52 in each arm.

5.2 If applicable, indicate how many subjects you expect to screen to reach your target sample (i.e. your screen failure rate).

#### Response:

All children with Diabetic ketoacidosis presenting to the John R. Oishei Children's Hospital (OCH) emergency department (ED) or transferred directly from outside facility to the pediatric intensive care unit (PICU) will screened for eligibility. Patients who are directly admitted to the PICU will represent 10% of the study sample with the remainder coming from the ED. As not all children in DKA are admitted to the PICU from the ED, it is estimated that approximately an additional 200 patients will be screened in the ER to achieve the target study size. In total, we anticipate screening approximately 310 patients with DKA for this study. 5.3 Justify the feasibility of recruiting the proposed number of eligible subjects within the anticipated recruitment period. For example, how many potential subjects do you have access to? What percentage of those potential subjects do you need to recruit?

Response:

Using historical patient volume data, it is estimated that approximately 2 years will be required to reach the target enrollment number.

# 6.0 Inclusion and Exclusion Criteria

6.1 Describe the criteria that define who will be **included** in your final study sample.

NOTE: This may be done in bullet point fashion.

Response:

Inclusion criteria:

- 1. Age between 0 and 18 years
- 2. Diagnosis of DKA from Type I DM:
  - a. Venous pH less than 7.25
  - b. Ketonuria as confirmed on urine point-of-care testing or urinalysis
  - c. Hyperglycemia (Serum glucose > 200 mg/dl)
  - d. Serum bicarbonate <15 mmol/L
- 3. Need for PICU admission based on clinical discretion
- 6.2 Describe the criteria that define who will be **excluded** from your final study sample.

*NOTE: This may be done in bullet point fashion.* 

#### Response:

Exclusion criteria:

- 1. Physician discretion for any reason not listed here
- 2. Septic or hypovolemic shock
- 3. Signs of life-threatening cerebral edema or multi-organ failure upon presentation to the emergency room or pediatric intensive care unit
- 4. More than 2 hours since arrival to the PICU or from first provider contact in the emergency room
- 5. Pregnancy
- 6. Type II DM
- 7. Elevated anion gap metabolic acidosis from another source other than ketoacidosis
- 6.3 Indicate specifically whether you will include any of the following special populations in your study using the checkboxes below.

*NOTE: Members of special populations may not be targeted for enrollment in your study unless you indicate this in your inclusion criteria.* 

- Adults unable to consent
- Individuals who are not yet adults (infants, children, teenagers)
- Pregnant women
- □ Prisoners
- 6.4 Indicate whether you will include non-English speaking individuals in your study. **Provide justification if you will exclude non-English speaking individuals.**

In order to meet one of the primary ethical principles of equitable selection of subjects, non-English speaking individuals may **not** be routinely excluded from research as a matter of convenience.

In cases where the research is of therapeutic intent or is designed to investigate areas that would necessarily require certain populations who may not speak English, the researcher is required to make efforts to recruit and include non-English speaking individuals. However, there are studies in which it would be reasonable to limit subjects to those who speak English. Some examples include pilot studies, small unfunded studies with validated instruments not available in other languages, studies with numerous questionnaires, and some non-therapeutic studies which offer no direct benefit.

#### Response:

Non-English speaking individuals will not be enrolled in this study. Spanish, Burmese, Somalian, Chinese, Russian, Arabic are the languages most likely to be spoken by the prospective subjects' legal guardian.

We expect to encounter a diverse group of non-English speaking legal guardians. The above list of languages does not include all non-English languages that we may encounter during our study recruitment phase.

We will not enroll non-English speaking subjects in this study as it is impractical for us to translate the consent documents in all conceivable languages. Meanwhile, it is impractical for us to have two people who speak the same non-English language during the recruitment phase with one being the person who obtains the consent and one being the witness per our IRB request at any given time.

By not including non-English speaking subjects in this study, we are not withholding any benefit from these patients. Meanwhile, we do not anticipate that we add any burden to the patients enrolled in the study.

The main purpose of this study is to compare the duration of acidosis after admission in children randomized to receive intravenous fluids containing normal saline to those receiving intravenous fluids containing lactated ringers during the treatment of DKA in the pediatric intensive care unit. Treating a DKA patient with normal saline or lactated ringers are currently both the standard of care at this institution. For a patient who is eligible and enrolled in the study, he/she will be randomized to receive either normal saline or lactated ringers in a controlled setting. For patients who meet study criteria that are not enrolled in the study, they will also receive either normal saline or lactated ringers or a mixture of both, depending on the treating physician's discretion. So regardless of whether a child with DKA is enrolled in the study or not, he/she will receive similar treatment.

Thus, we will exclude subjects whose legal guardians do not speak English from the study due to the above mentioned reasons. We believe that we will not withhold any benefit from non-participants, nor add undue burden to the participants by not enrolling non-English speaking patients in the study.

# 7.0 Vulnerable Populations

If the research involves special populations that are considered vulnerable, describe the safeguards included to protect their rights and welfare.

*NOTE:* You should refer to the appropriate checklists, referenced below, to ensure you have provided adequate detail regarding safeguards and protections. You do not, however, need to provide these checklists to the IRB.

7.1 For research that involves **pregnant women**, safeguards include: NOTE CHECKLIST: Pregnant Women (HRP-412)

Response:

- $\boxtimes$  N/A: This research does not involve pregnant women.
- 7.2 For research that involves **neonates of uncertain viability or non-viable neonates,** safeguards include: NOTE CHECKLISTS: Non-Viable Neonates (HRP-413), or Neonates of Uncertain Viability (HRP-414)

Response:

- ☑ N/A: This research does not involve non-viable neonates or neonates of uncertain viability.
- 7.3 For research that involves **prisoners**, safeguards include: NOTE CHECKLIST: Prisoners (HRP-415)

Response:

- $\boxtimes$  N/A: This research does not involve prisoners.
- 7.4 For research that involves **persons who have not attained the legal age for consent to treatments or procedures involved in the research ("children")**, safeguards include: NOTE CHECKLIST: Children (HRP-416)

Response:

We will obtain consent from legal guardians.

■ N/A: This research does not involve persons who have not attained the legal age for consent to treatments or procedures ("children").

7.5 For research that involves **cognitively impaired adults**, safeguards include: NOTE CHECKLIST: Cognitively Impaired Adults (HRP-417)

Response:

- $\boxtimes$  N/A: This research does not involve cognitively impaired adults.
- 7.6 Consider if other specifically targeted populations such as students, employees of a specific firm, or educationally or economically disadvantaged persons are vulnerable. **Provide information regarding** *their safeguards and protections, including safeguards to eliminate coercion or undue influence.*

Response:

No other specially targeted populations will be enrolled in this study.

